7.6 Data Management

All data collected for the study should be recorded accurately, promptly, and legibly. For primary data collection, the investigator or qualified designee is responsible for recording and verifying the accuracy of subject data. For data not obtained from a primary source (i.e., secondary data, such as claims and electronic health records), the investigator is responsible for reviewing data quality and relevance to the best of the investigator's knowledge. By signing this protocol either electronically or written, the investigator confirms that the quality and relevance of data has been assessed to meet the minimum requirements for all study objectives. If this study has been outsourced, the institutional policies of the supplier should be followed for development of data management plans. However, the supplier should ensure compliance with Good Pharmacoepidemiology Practice, and all applicable federal, state, and local laws, rules and regulations relating to the conduct of the study.

Data Management Software and Hardware:

Statistical analyses will be implemented using relevant software, including SAS or R.

Description of Data Preparation and Methods for Data Retrieval and Collection:

The investigator will review all documentation related to data preparation, retrieval, and cleaning. Detailed descriptions of data processing, including abstraction, curation, quality assurance, and quality checks will be provided once a supplier has been selected.

7.7 Programming Quality

This study will incorporate the following quality checks for data analysis and reporting programming:

- Creating a program requirements and specification (PRS) document

PRODUCT: MK-3475	PROTOCOL/AMENDMENT VERSION NO.: 00-v03
REVOPS ID NO: NIS104408	NIR DRC APPROVAL DATE: 11/24/2025
EPIDEMILOGY NO.: EP05026.164	

- Developing and testing of statistical programs which includes ensuring the programs run successfully and all output are reviewed to ensure they meet the criteria included in the PRS. This includes validating that all inputs (metadata or parameter values) are correctly specified in the programs and are consistent with the PRS.
- Independent Review and Testing, conducted by a second programmer to ensure that the input and outputs of the programs created by the first programmer meet the documented PRS. This includes the activities listed below. If discrepancies are found, the programmers will discuss and repeat steps until consistency is achieved.
 - Review of code to ensure the program aligns with the PRS
 - Execution of code and review of results for some or all scenarios
And may include the following activity:
 - Parallel programming of a small piece of critical code
- Review of outputs/results to ensure accuracy and format of each deliverable.

7.8 Data Analysis

Data analyses will be conducted through 4Q2027. Operational details further defining variables, analytic methodology, and table shells will be defined in a separate detailed statistical analysis plan.

Analysis Plan

The primary study objectives will require four study cohorts to evaluate the real-world effectiveness of pembrolizumab in US NSCLC patients across racial, ethnic, and age groups:

1. Early-stage patients treated with pembrolizumab monotherapy,
2. Early-stage patients treated with pembrolizumab in combination with PBC,
3. Advanced-stage patients treated with pembrolizumab monotherapy, and
4. Advanced-stage patients treated with pembrolizumab in combination with PBC

For each of the four study cohorts, sociodemographic and clinical characteristics among NSCLC patients receiving pembrolizumab in a real-world setting will be described among racial, ethnic, and age groups. For categorical variables, frequencies, and percentages will be generated. For continuous variables, descriptive statistics will include means, standard deviations, medians, interquartile ranges, and/or minimum and maximum values, as applicable. The number of patients with unknown values for both categorical and continuous variables will be provided. Given the descriptive nature of the study, no statistical testing will be performed.

PRODUCT: MK-3475	PROTOCOL/AMENDMENT VERSION NO.: 00-v03
REVOPS ID NO: NIS104408	NIR DRC APPROVAL DATE: 11/24/2025
EPIDEMIOLOGY NO.: EP05026.164	

Real-world OS as defined in Section 7.3.2 will be estimated among patients using Kaplan-Meier methods. Median survival times and the probabilities of survival at key milestones of interest (e.g., 1-year, 5-year, etc.) and corresponding 95% confidence intervals (CI) will be calculated. Separate analyses will be conducted for each the following subgroups: Black or African American, Asian, other race, White, Hispanic/Latino, not Hispanic/Latino, elderly (≥ 75 years), and younger (<75 years). Racial subgroups with small sample sizes (<75 patients) may be combined with 'other race'. A descriptive summary of rwOS estimates will be provided for all races, ethnicities, and age groups. Given the descriptive nature of the study, no imputation for missing data or statistical testing will be performed. Sensitivity analyses may be conducted to evaluate the effectiveness of pembrolizumab among the subset of patients receiving pembrolizumab in line with currently approved indications (i.e., on-label use).

Exploratory analyses of rwDFS and rwEFS as defined in Section 7.3.2 will be conducted in the early-stage NSCLC population. The rwDFS endpoint will be evaluated among patients analyzed in Primary Objective 1 (i.e., surgically-resected patients who did not receive neoadjuvant therapy prior to surgery). The rwEFS endpoint will be evaluated among patients analyzed in Primary Objective 2 (i.e., resectable patients who received neoadjuvant therapy). For both outcomes Kaplan-Meier methods will be used to estimate median survival times and the probabilities of survival at key milestones of interest and corresponding 95% CI will be calculated. Separate analyses will be conducted for each race, ethnicity, and age group. Sensitivity analyses may be conducted to evaluate the effectiveness of pembrolizumab among the subset of patients receiving pembrolizumab in line with currently approved indications.

An exploratory analysis of rwOS using propensity score weighting methods will be conducted in the advanced NSCLC population to balance baseline characteristics that may confound the effect of each exposure group (i.e., race, ethnicity, or age group) on survival following pembrolizumab treatment. Due to sample size limitations, propensity score methods will not be applied to the early-stage population. Propensity scores will be estimated using multinomial logistic regression for multiple group comparisons (i.e., race) and logistic regression for binary group comparisons (i.e., ethnicity or age group), incorporating covariates associated with group membership and/or the outcome of interest. The selection of covariates to be used for propensity scoring will be determined based on subject-matter expertise, a review of published literature, and results of the completed feasibility assessment. Covariates must have minimal missingness and may include variables such as sex, ECOG performance status, smoking status, disease stage at initial diagnosis, histology, PD-L1 status, brain metastasis, age (for the analyses of race and ethnicity), and race (for the analysis of age). If a covariate could also act as a mediator (i.e., lies along the causal pathway by which race, ethnicity, or age influence survival), it will be excluded from propensity scoring. Missingness may be considered as a separate category for each covariate. The final propensity score model will be selected based on model stability, parameter estimation accuracy, and the distribution of predicted propensity scores. Models showing extreme propensity score distributions (values approaching 0 or 1) or poor parameter estimation will

PRODUCT: MK-3475	PROTOCOL/AMENDMENT VERSION NO.: 00-v03
REVOPS ID NO: NIS104408	NIR DRC APPROVAL DATE: 11/24/2025
EPIDEMIOLOGY NO.: EP05026.164	

be considered inadequate, and alternative model specifications will be evaluated. Once estimated, the propensity scores will be used to create balanced comparisons between subgroups using an appropriate weighting method, such as inverse probability weighting (IPW). Weights will be derived from the marginal distribution of covariates in the entire cohort, so that each group more closely resembles the overall study population. Stabilized weights will be applied to reduce the influence of extreme weights and improve precision of estimates. Covariate balance will be assessed using standardized mean differences (SMD) before and after propensity score adjustment. An absolute SMD < 0.1 will be considered indicative of adequate balance. Additional balance diagnostics may include overlap assessment through propensity score distribution plots, variance ratios for continuous variables, and Kolmogorov-Smirnov tests for distributional balance. If adequate balance is not achieved through the initial approach, alternative weighting strategies or adjustments to covariate inclusion will be explored. Following propensity score adjustment, rwOS outcome analyses will be conducted on the balanced pseudo-population. Weighted Kaplan-Meier estimators will be used to generate median survival times and probabilities of survival at key milestones along with 95% CI, separately for each treatment type.

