Population	Adults (≥ 18 years of age) diagnosed with early-stage or advanced NSCLC	Prior treatment with an IO agent or an investigational drug Treatment with pembrolizumab in combination with any of the following: concurrent chemoradiation therapy; radiation therapy, or an investigational drug
Intervention	Received pembrolizumab (monotherapy or in combination with platinum-based chemotherapy [PBC]) for the treatment of NSCLC	Participation in clinical trials for NSCLC before pembrolizumab Treatment with pembrolizumab in the second-line setting or later
Comparison	No formal statistical comparisons	
Outcomes	Real-world overall survival (rwOS) among the following subgroups: 
 Race (e.g., Black or African American, Asian, other [American Indian/Alaska Native, Native Hawaiian/Other Pacific Islander, and other race] and White patients) Hispanic/Latino ethnicity (Hispanic/Latino patients and not Hispanic/Latino patients) Age (elderly patients ≥ 75 years and younger patients < 75 years) Real-world disease-free survival (rwDFS) in early-stage NSCLC patients (exploratory) Real-world event-free survival (rwEFS) in early-stage NSCLC patients (exploratory)	
Time	Patients initiating pembrolizumab between October 2, 2015 (first FDA approval of pembrolizumab for NSCLC) and June 30, 2025 (allows patients to accumulate ≥ 2 years of follow-up time to adequately assess rwOS); Data cutoff planned June 30, 2027	
Study design	Retrospective cohort study using structured EHR-derived data	

PRODUCT: MK-3475	PROTOCOL/AMENDMENT VERSION NO.: 00-v03
REVOPS ID NO: NIS104408	NIR DRC APPROVAL DATE: 11/24/2025
EPIDEMIOLOGY NO.: EP05026.164	

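### Stabilized weights cannot do what Section 7.8 claims: in group-specific weighted Kaplan-Meier curves the stabilizing constant cancels, so they neither curb extreme weights nor improve precision

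*Protocol*

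**What the plan says.** Section 7.8 of the Protocol fixes three things for the weighted analysis of real-world overall survival in advanced NSCLC.

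- **Target:** "Weights will be derived from the marginal distribution of covariates in the entire cohort", so that each group resembles the whole study population. Inverse probability weighting is given as an example of the method.
- **Device against extreme weights:** "Stabilized weights will be applied to reduce the influence of extreme weights and improve precision of estimates".
- **Output:** "Weighted Kaplan-Meier estimators will be used to generate median survival times and probabilities of survival at key milestones along with 95% CI", separately by treatment type. No pooled model, hazard ratio or contrast is named, and Table 1 (Section 6) lists "No formal statistical comparisons".

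Other provisions touch the same problem. On the propensity model, Section 7.8 says: "Models showing extreme propensity score distributions (values approaching 0 or 1) or poor parameter estimation will" "be considered inadequate, and alternative model specifications will be evaluated". On balance it says: "If adequate balance is not achieved through the initial approach, alternative weighting strategies or adjustments to covariate inclusion will be explored"; the threshold is an absolute standardized mean difference (SMD) of 0.1. Overlap plots are optional. Race groups under 75 patients are pooled (Sections 7.3.3 and 7.8). Section 7.10 admits that weighting may cost precision.

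**The concern.** Stabilization is the one measure that the protocol says will limit extreme weights. It has a real role when groups enter a common weighted model, because it stops a rare group from being scaled up to the size of the whole cohort. A Kaplan-Meier curve estimated inside one group makes no use of that scale. If the measure is inert for the stated output, readers of the minority-group results will believe that extreme weights have been dealt with when they have not.

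It matters most for small groups. Reweighting a group that is 2-5% of the cohort to the covariate mix of everyone is where a few patients can carry much of the estimate, and these groups are the reason for the study.

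**Working it through.** **Inputs.** Table 2, advanced NSCLC, before the split by treatment type: Asian 531, Black 2,737, White 17,298; Hispanic 918, not Hispanic 18,802. Median survival of 1.67 years from Section 7.5. The protocol gives no figure for the weighted analysis, so there is none to reproduce.

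**Step 1: the stabilizing factor.** For a patient in group g with fitted score e, the unstabilized weight is w = 1/e and the stabilized weight is P(g)/e = c × w, with c = P(g) the same for everyone in the group.

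- Asian: 531 / (531 + 2,737 + 17,298) = 531 / 20,566 = 0.026
- Hispanic: 918 / (918 + 18,802) = 918 / 19,720 = 0.047

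With all 25,623 treated patients as denominator, unknowns included, these are 0.021 and 0.036. Within one treatment type, c becomes P(g | treatment), which is still constant in each cell.

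**Step 2: cancellation.** The weighted curve is S(t) = product over event times of [1 − (sum of w over deaths) / (sum of w over those at risk)]. Replacing w by c × w multiplies both sums by c, so every factor, and hence every median and milestone probability, is unchanged. The constant also cancels in:

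- effective sample size (ESS), (sum w)² / (sum w²);
- the largest patient's share, max w / sum w;
- a Greenwood variance that uses the effective risk set (sum w)² / (sum w²);
- each bootstrap resample, where c may be re-estimated but still drops out.

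It does not cancel in a Greenwood formula that treats weights as counts.

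**Step 3: numerical illustration.** Simulated race groups in the Table 2 proportions, with a fitted multinomial logistic score and exponential survival with baseline median 1.67 years. Six covariates were used, three of them related to Asian membership with assumed log-odds of 0.3 (mild), 0.6 (moderate) or 1.0 (strong). One data set was drawn per scenario. Asian group, with standard errors (SE) for 1-year survival:

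| Scenario | n | Median (y) | 1-year survival | ESS | Largest share | Weight-adjusted SE | Count-type SE, unstabilized → stabilized |
|---|---|---|---|---|---|---|---|
| Mild | 518 | 1.717 | 0.669 | 429 | 0.6% | 0.0230 | 0.0033 → 0.0207 |
| Moderate | 540 | 1.759 | 0.723 | 188 | 3.9% | 0.0342 | 0.0031 → 0.0191 |
| Strong | 508 | 1.608 | 0.618 | 89 | 3.8% | 0.0542 | 0.0035 → 0.0225 |

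Every column except the last is the same with and without stabilization. In the moderate case the largest weight falls from 812.08 to 21.32, but the sum falls from 20,919 to 549.27, and 812.08 / 20,919 = 21.32 / 549.27 = 3.9%.

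**Step 4: the count-type interval.** Stabilized count-type SE over weight-adjusted SE: 0.0207 / 0.0230 = 0.90, 0.0191 / 0.0342 = 0.56, 0.0225 / 0.0542 = 0.41 (unrounded inputs give the same ratios to two decimals, the last being 0.415). Stabilization widens this interval, which is not a gain in precision, and leaves its SE 10%, 44% and 59% too small.

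**Step 5: what the other safeguards detect.** Alternative weighting is triggered by the SMD, which can be below 0.1 while a few patients hold much of the weight. Pooling acts on headcount and on race only; the strong scenario has 508 patients, well above 75, but an ESS of 89. A logistic or multinomial model with intercept fitted by maximum likelihood has a mean fitted score equal to group prevalence, so scores near 0 are expected for a 2-5% group even when the model is right.

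**The case against.** The best reply is that the plan does not rest on stabilization alone. A reader might infer that small groups have no protection at all, and the text does not support that. Score distributions are reviewed and models respecified, overlap plots may be drawn, other weighting is available if balance fails, small race groups are pooled, the early-stage cohort is kept out of the method, and the loss of precision is acknowledged. These are weak for this purpose, but they exist.

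A reader might also infer that the rule on scores near 0 or 1 rejects every model for a rare group. It sets no cutoff, speaks of extreme distributions, and stands beside model stability and parameter estimation, so it need not. What remains is that the phrase is hard to apply to rare groups; for age (12,922 against 12,701) the difficulty does not arise.

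Stabilization is also not wholly without effect: under a count-type variance it removes most of a gross understatement of the SE. That holds, but it neither improves precision nor makes the interval valid, and the protocol does not say that such a variance will be used.

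Finally, truncation limits and variance methods commonly sit in the separate statistical analysis plan, and their absence here is no fault. The point is different: the protocol states a benefit that the method cannot deliver for the stated estimator, and an analysis plan that follows the sentence would inherit the error.

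**Conclusion.** The point holds as a correction of a wrong statement. For group-specific weighted Kaplan-Meier curves, stabilized and unstabilized inverse probability weighting are the same analysis. This is exact and needs no simulation. It assumes the usual numerator without covariates, which fits the whole-cohort target in Section 7.8, and no pooled weighted model, which is what the section describes.

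How much extreme weights would matter is not known from the protocol. Under the assumed covariate strengths, the Asian ESS ran from 429 of 518 to 89 of 508. These figures show a range and do not predict the study's results.

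The remaining safeguards do not directly detect a few patients dominating a small group. The consequence is confined to Exploratory Objective 2 in advanced NSCLC; the four primary objectives use unweighted Kaplan-Meier estimates and are untouched.

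**What to change.** In Section 7.8, remove the claim that stabilization limits extreme weights or improves precision. In its place, with details in the statistical analysis plan if preferred:

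- name a device that acts within group, for example truncation at a prespecified within-group percentile, with untruncated results shown alongside and the SMDs rechecked after truncation;
- compute the 95% CIs with a robust variance, or with a bootstrap that re-estimates the propensity score in each resample;
- report effective sample size and the largest patient's share of total weight for each group;
- judge scores near 0 or 1 relative to the prevalence of the group.

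If overlap weighting is named as a fallback, state that it changes the target population from the overall cohort, so its results answer a different question from the one in Section 7.8.

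The cost is a wording change and modest programming, well before the June 2027 data cutoff. The downside is that truncation may leave slight imbalance, which the SMD recheck would show.

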7.9 Quality Control

By signing this protocol, all parties agree to following applicable standard operating procedures (SOPs). All parties also agree to ensuring all existing and new study personnel are appropriately trained to ensure the study is conducted and data are generated, documented, and reported in compliance with the protocol, Good Pharmacoepidemiology Practice (GPP), Good Pharmacovigilance Practices (GVP), and all applicable federal, state, and local laws, rules and regulations. All parties should maintain transparency and open communication in order to effectively manage the study and proactively mitigate any risks.

The Sponsor may conduct routine or for-cause audits to ensure oversight and conduct of the study are completed in accordance with the protocol, quality standards (e.g., GPP and GVP), and applicable laws and regulations. If a significant quality issue (SQI) is identified at any time during the conduct of the study, it must be escalated to the Sponsor immediately. A SQI is any issue with the potential to negatively impact, either directly or indirectly, the rights, safety and well-being of patients or study participants and/or the integrity of the data. In the event an audit or SQI results in corrective or preventive actions, all parties are expected to appropriately implement the action plan in a timely manner.

Flatiron Health will conduct all activities related to developing and ensuring the quality of the real-world dataset for this research study. This includes the selection of patients for the study cohort and the inclusion of relevant data variables. Flatiron will also manage all activities involved in ensuring the quality and delivery of the data, including database creation, approval by central IRB, quality assurance of data, and building and securely transmitting the data files to Sponsor.

Flatiron Health will comply with the audits described under this section in accordance with Flatiron Health's contract with Sponsor for this study, and Flatiron Health will support

PRODUCT: MK-3475	PROTOCOL/AMENDMENT VERSION NO.: 00-v03
REVOPS ID NO: NIS104408	NIR DRC APPROVAL DATE: 11/24/2025
EPIDEMIOLOGY NO.: EP05026.164	

quality assurance verification activities as reasonably requested by Sponsor, or a third party on behalf of Sponsor. Additionally, auditors/inspectors will be limited to reviewing documentation specific to this study in accordance with Flatiron Health's policy regarding confidential information.

7.10 Limitations of the Research Methods

Validity and interpretability of measurement:

- EHR-derived data are frequently collected for the purpose of the clinical management of oncology patients and not primarily for research purposes. The proposed study is subject to data that are available in the selected database and the level of granularity provided for available data.
- OS estimates may be biased due to possible misclassification of events resulting from incomplete or low sensitivity mortality data. However, the mortality data in the secondary data sources proposed for this study are enhanced by linking multiple data sources including data abstraction from EHR, SSDI, and obituaries, and the mortality variable used in the FHRDs has been shown to have high sensitivity (>90%) when compared to the National Death Index [Curtis, M. D., et al 2018] [Zhang, Q., et al 2021]. Validation of the mortality endpoint is one of the required criteria needed to select the data source used for the study.
- OS estimates may be biased due to uncontrolled confounding factors, including those that are available in the dataset (e.g., stage, treatment setting, year of diagnosis) and those that are not available in the dataset (e.g., age-related comorbidities). An exploratory analysis using propensity score weighting methods will attempt to balance confounders across subgroups using available covariates. It should be noted that the use of propensity score weighting may result in less precise effect estimates.
- Combining racial/ethnic minorities does not capture the heterogeneity that may exist within individual races or ethnicities. Individual racial groups will remain separate to the extent possible given sample size limitations.

Data completeness:

- As is common with observational studies utilizing real-world data, the main limitations for this study include lack of availability of data on certain variables and missingness in data obtained from the EHR. Certain variables may not be available with full completeness, such as race/ethnicity and treatment details.
- Additionally, patients may seek care outside of the supplier's network. This may contribute to missing, incomplete data and patient loss to follow-up.

PRODUCT: MK-3475	PROTOCOL/AMENDMENT VERSION NO.: 00-v03
REVOPS ID NO: NIS104408	NIR DRC APPROVAL DATE: 11/24/2025
EPIDEMIOLOGY NO.: EP05026.164	

Study design:

- Although the same patient may be present in both eNSCLC and aNSCLC FHRD databases, the exclusion criteria pertaining to prior treatment ensure that each patient will only be included in the study sample once. Patients included in the eNSCLC FHRD who received pembrolizumab in both the early- and advanced-stage settings will only be included if they meet all eligibility criteria at earliest initiation of pembrolizumab (i.e., in the early-stage setting), while patients included in the aNSCLC FHRD who have evidence of treatment with pembrolizumab in both the early- and advanced-stage settings will not be included.
- Study inclusion/exclusion criteria are intended to reflect a real-world patient population. As such, study populations may not mirror the corresponding clinical trial populations and, as a result, observed results may not be comparable to those reported using clinical trial data. Sensitivity analyses may be conducted to evaluate the effectiveness of pembrolizumab among subsets of patients receiving pembrolizumab in line with currently approved indications (i.e., on-label use).
- Mortality data may not have sufficient maturity for all patients. For example, OS among patients with early-stage NSCLC recently treated with pembrolizumab may be particularly likely to be impacted by limited data maturity, affecting interpretability. Exploratory outcomes rwEFS and rwDFS will be evaluated for early-stage patients to mitigate the limitation in data maturity. Since neither outcome has been validated for use in the eNSCLC FHRD, results should be interpreted with caution.

Generalizability of study results:

- The data source may not be representative of the overall US NSCLC population. Of note, the eNSCLC FHRD and aNSCLC FHRD are similar databases that select probabilistic samples of patients diagnosed with eNSCLC or aNSCLC from practices in the FHRN. The eNSCLC FHRD samples approximately 17% of patients diagnosed with eNSCLC from the FHRN, while the aNSCLC FHRD samples approximately 52% of patients with aNSCLC from the FHRN. Consequently, a pooled sample combining patients from both databases will include a higher proportion of patients treated in the advanced setting than would a representative sample. There is evidence that the aNSCLC FHRD share a similar demographic and geographic distribution with the US Surveillance, Epidemiology, and End Results program (SEER) program and the National Program of Cancer Registries (NPCR) [Ma, X., et al 2020], but study results may not be generalizable to NSCLC patient populations globally due to variation in patient demographic and clinical characteristics and standard of care.
- OS estimates may be biased due to confounding factors that may not be available in the dataset (e.g., socioeconomic status, age-related comorbidities, etc.).

PRODUCT: MK-3475	PROTOCOL/AMENDMENT VERSION NO.: 00-v03
REVOPS ID NO: NIS104408	NIR DRC APPROVAL DATE: 11/24/2025
EPIDEMIOLOGY NO.: EP05026.164	

